Title	A pilot proof of concept, single site study to assess the effect of exoskeletal support on motor control strategies in individuals with stroke
Short Title	Exoskeletal support in stroke
Brief Summary	This interventional study will measure motor performance, including 3D movement analysis and muscle activity, in response to exoskeleton assistance. The cohort design will compare stroke patients to healthy controls. Data collection will be conducted in a single, 2-hour session. We will also access stroke patients' brain MRIs that were obtained as standard of care during acute admission for stroke.
Phase	Pilot
Objectives	The primary objective is to examine in a VR environment whether additional gravity compensation from exoskeletal support will improve bimanual coordination in stroke patients. A second primary objective is to determine intervention effects on muscle control processes underlying bimanual coordination. As a secondary objective, we aim to correlate these measures with measures of stroke lesion characteristics.
Methodology	Cohort design
Endpoint	The primary endpoints will be a 2% increase in RC and a 5% decrease in MC. The secondary endpoint will be a significant relationship between the change in MC (% decrease in MC) and CSTLL with an R^2 value greater than 0.4
Study Duration	12 months
Participant Duration	One, 2-hour session
Duration of IP administration	Approximate 15 minutes
Population	24 participants; 12 with history of stroke more than 6-months prior to enrollment, 12 healthy age- and gender-matched controls. Males and females 18-years old and older from with and without diagnosis of stroke.
Study Site	Single-center (NYULMC)
Number of participants	24
Description of Study Agent/Procedure	We use a custom designed and built exoskeleton device that applies a torque to both shoulders. Torque values do not exceed 50% of the torque due to gravity. The device is mounted to a testing chair and attached to the participant using Velcro straps.
Reference Therapy	N/A
Key Procedures	No clinical procedures are required
Statistical Analysis	Inferential group statistics (t-test, mixed design ANOVA); correlation, linear regression

Schematic of Study Design

1 Key Roles

Principal Investigator

[name], Associate Professor
NYU Grossman School of Medicine
[name]
T [contact] (ACC)
[contact]

Study Investigator

[name], Postdoc
[name]
[contact]
[contact]

2 Introduction, Background Information and Scientific Rationale

2.1 Background Information and Relevant Literature

Stroke is the 5th leading cause of death in the United States, and nearly 8 million Americans report it as their primary cause of disability (Virani et al., 2021). Of particular concern is that 38% of stroke survivors report major difficulty in using their impaired arm (Duncan et al., 2003). Recent advances in rehabilitation sciences have identified learned non use as a potential mechanism by which hemiparetic stroke survivors limit use of their impaired limb (Taub et al., 2006). Therapy programs such as constraint-induced movement therapy (CIMT) have been developed to counter learned non use; however, these therapies have failed to show sustained benefits likely due to time, expense, and the lack of bimanual training tasks (Kwakkel et al., 2015; Wolf et al., 2006). Therefore, there exists a critical need for new stroke therapies that are cost effective and allow for robust bimanual coordination.

Our innovative approach uses virtual reality (VR), in conjunction with custom-built exoskeletons, to provide stroke patients with the task and environmental factors needed to increase use of their paretic limb. Therefore, the long-term goal of this work is to develop device-based rehabilitative platforms that promote impaired arm use in chronic stroke. VR based applications have emerged as new treatment approaches in stroke rehabilitation settings over the last ten years. One of the most important advantages that a VR system can provide is that it allows researcher to create visual environments which surround the user to in a way that cannot be possible in physical reality. For example, by encouraging shared control of a virtual object, it is possible to couple the hands to promote increased use of the paretic limb during reaching (Diedrichsen, 2007).

We also use a custom-built exoskeleton to provide assistance to the impaired arm in stroke patients. Specifically, the exoskeleton provides gravity compensation, a process where the force of gravity is canceled out, fully or partially, by the exoskeleton mechanics (Chen et al., 2019). Exoskeletons have been used for research purposes for decades, and emerging clinical applications are at the forefront of motor impairment rehabilitation sciences (Collins et al., 2015; Gueye et al., 2021; Keeling et al., 2021).

Our current understanding of the combination of VR and exoskeleton modalities to improve arm function in stroke is lacking. The specific aim of this study is to determine if gravity compensation, via exoskeleton loading, can increase impaired arm use in stroke participants during a VR reaching task. This study will advance the field of stroke rehabilitation by demonstrating the feasibility of shared-control reaching tasks in VR as a potential therapeutic solution for upper extremity stroke impairment.

Recently, we completed a feasibility study in which we show our protocol is safe and effective in altering limb coordination in 12 healthy control subjects (Brunfeldt et al., 2022). Moreover, we completed a study in 14 chronic stroke survivors and found they tolerated the procedures without incident (Brunfeldt et al., 2023, *in review*). Our study in stroke survivors additionally shows that integrity of the corticospinal tract is associated with motor performance in our task. This paves the way for mechanistic approaches to neuroimaging biomarker studies (Cassidy et al., 2018; Stinear, 2017; Zhu et al., 2010).

2.2 Name and Description of the Investigational Agent

The investigational agent is a custom designed and built exoskeleton device. The device, detailed in section 6, is not commercially available, is not registered with the FDA and does not have an IND or IDE status.

The device is a wearable, non-implantable exoskeleton designed to provide gravity compensation. Gravity compensation is defined as the application of torque to the shoulder that counteracts the torque due to gravity. That is, the torque vs. angle profile is equal and opposite to that of gravity. For the purposes of this study, we will only use a 50% gravity compensation (i.e., the magnitude of torque is 50% that of gravity). The purpose of the device is to assist stroke participants while they reach for virtual objects in a VR environment.

2.2.1 Preclinical Data

The study investigator, [name], recently completed a study at the MedStar Health Research Institute (STUDY00004671) using these devices on 14 stroke participants. We did not find a significant change in RC or MC (primary endpoints) at the group level. However, we did find individual differences in outcomes that could be explained by lesion characteristics. Specifically, stroke participants with more overlap between the lesion and the corticospinal tract had a smaller change in muscle activity during exoskeletal support compared to no exoskeletal support (Brunfeldt et al., *in review*). We did not observe any adverse event.

2.2.2 Clinical Data to Date

N/A. No clinical data to date.

2.2.3 Dose Rationale

The 50% gravity compensation level was selected based on previous research in healthy controls (Brunfeldt et al., 2022) and our recently completed study (Brunfeldt et al., *in review*). In both studies, 50% was sufficient to change arm coordination and was well tolerated by participants.

2.3 Rationale

This study is aimed at evaluating whether additional gravity compensation using an exoskeleton device will improve bimanual coordination chronic stroke survivors. The study addresses key limitations such as allowing participants to use both arms to perform activities of daily living, opposed to the traditional impaired-only approach in CIMT. Our study also allows for the identification of neuromuscular mechanisms of arm control in stroke. Specifically, we hypothesize that exoskeleton loading will increase reaching distance of the impaired arm while simultaneously decreasing the amount of muscle activity required. Our initial studies show individual differences in each participant's responsiveness to our device. Therefore, we hypothesize that there is a relationship between motor performance and lesion characteristics such as size and location of the stroke infarct. Our cohort design allows us to compare motor performance between stroke survivors and age-matched healthy controls. This allows us to test specific predictions from the optimal feedback control theory (OFCT) approach to movement (Todorov & Jordan, 2002). Specifically, we can identify each participant's sensitivity to different forms of sensory feedback (e.g., vision vs. proprioception). This information is critical in developing personalized device-based rehabilitation protocols. There are no specific problems associated with using healthy controls as a control group. We will take every precaution to ensure demographic balancing between groups.

2.4 Potential Risks & Benefits

2.4.1 Known Potential Risks

Potential risks of the exoskeleton include arm fatigue and soft-tissue (e.g., muscle, skin) discomfort. Fatigue is not greater than minimal risk because the arm movements will mimic reaching for an object on a shelf at eye level. No more than 54 reaches will be made in any single testing block, and these reaches are self-paced. Soft-tissue discomfort may arise from the exoskeleton applying a force to the arm. Discomfort poses no greater than minimal risk because the participant will only wear the device for approximately 5 minutes during the data collection phase. Also, the magnitude of force applied to the arm is no more than 50% of that due to gravity. The upper arm weighs approximately 5.77% of body weight ((Plagenhoef et al., 1983). For example, a 150 lbs. person would receiving a loading amount to counter 8.65 lbs. of force. The exoskeleton device will be worn during all testing blocks, however, the load is only applied during the 'loading phase' which lasts approximately 5 minutes.

It is anticipated that participants may be inconvenienced by the amount of time necessary to complete the study and may experience fatigue because of completing required reaching tasks in the VR system. Very rarely, participants may experience short-term dizziness or headache because of using the head mounted display of the VR system. Participants will be given ample time for practice and rest, and they may take a break and/or discontinue the study at any time.

To limit the risks associated with VR headset and exoskeleton use, we will provide the participant with breaks every 5-minutes. Also, all reaches will be self-paced. Participants will be verbally instructed that they may request unscheduled breaks during the data collection blocks. These unscheduled breaks will not affect data integrity. We also use padding and elastic gauze on the arms to reduce pressure and abrasion risk.

There is a potential risk of breach of confidentiality. To mitigate this, procedures will be carried out in a laboratory space on the NYULMC campus. We are requesting personal health information from the patient's medical record. To mitigate this, access will only be granted to named persons on this protocol; data will be stored on TrialMaster.

2.4.2 Known Potential Benefits

There is no direct benefit to individual study participants.

Information gained in this study will inform the next generation of rehabilitative therapies for chronic stroke survivors. The potential benefits to the stroke community outweigh the potential risks to participants due to participants' exposure to no more than minimal risk.

This study aims to explore the optimal control strategies implemented during reaching. As learned nonuse represents a maladaptive compensation in response to upper extremity dysfunction, targeted rehabilitative therapies that rebalance the effort required for reaching may provide clinicians with additional tools for treating chronic stroke. While this study cannot address the probability, magnitude, or duration of potential benefits, we expect a future iteration of these procedures could help the nearly 8 million stroke survivors living with disability.

3 Objectives and Purpose

3.1 Primary Objective

To identify the effects of gravity compensation from exoskeletal support on bimanual coordination in stroke participants during a reaching task in VR. Specifically, we will determine if gravity compensation can increase the reaching displacement of the impaired arm relative to the non-impaired arm. We will compare stroke participant performance to healthy controls to determine if stroke influences an individual's kinematic responsiveness to exoskeletal support.

To determine the effects of gravity compensation from exoskeletal support on bilateral muscle activity in stroke participants. Specifically, we will determine if gravity compensation can reduce the required muscle activity needed to perform the VR reaching task. We will compare stroke and healthy control participant muscle activity to determine if stroke influences an individual's neuromuscular responsiveness to exoskeletal support.

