4.1 Description of Study Design

In this study, we aim to use a virtual reality reaching task with exoskeletons to increase use of the impaired limb in stroke survivors. For all participants, they will complete 3 blocks of 54 trials in a single session. Block 1 is a baseline phase where subjects will perform reaches without any loads applied via the exoskeleton devices. Block 2 is the intervention block where bilateral exoskeletons apply gravity assistance to the impaired arm for stroke survivors and gravity resistance to the non-impaired arm. In healthy controls, assistance is applied to the non-dominant arm and resistance is applied to the dominant arm. Block 3 is a retention block, where tested procedures are identical to block 1.

Virtual Reality Task

In each block, the subject will be asked to sit on a chair, wear the Oculus headset, and hold a touch controller in each hand to reach through a target displayed in the VR system (Figure 1). Subjects can see two avatar's hands, representing their own hands movements, in the VR environment. Each experimental block includes 54 trials. In each trial, the subject is asked to put his/her hands on his/her laps as a starting position. After the start position is achieved, a target cube will show up in the VR environment and the subject will use both hands to reach the cube. A cursor, located at the midpoint of the hands, will be used to 'hit' the target cube during each trial. The same horizontal locations of the targets used in a previous VR study will be used (Wang et al., 2021). Target locations will span the workspace from approximately ± 15 degrees located at shoulder and eye level. This distribution is chosen to simulate reaches typically made in activities of daily living. The sequence of target locations will be randomized. Subjects' hand movements will be confined to a quadrant and the radius will be scaled to each subject's arm length, within the subject's comfortable range of motion. Subjects can move at their own comfortable speed.

Figure 1: Oculus Rift headset and touch controller bundle

Exoskeleton device

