4.2 Study Endpoints

4.2.1 Primary Study Endpoints

The primary endpoints will be a 2% increase in RC and a 5% decrease in MC. These values are taken from (Brunfeldt et al., 2022).

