10.2 Statistical Hypotheses

Primary endpoint. Exoskeletal support will increase RC in stroke participants. Paired t-test comparing RC from baseline to loading blocks.

Primary endpoint. Exoskeletal support will decrease MC in stroke participants. Paired t-test comparing MC from baseline to loading blocks.

Secondary endpoint. There will be an association between change in RC (or MC) and CST lesion load. Independent linear regressions (RC vs. CSTLL and MC vs. CSTLL).

Secondary endpoint. RC values in stroke participants will be less than RC values in healthy controls during baseline blocks (t-test). MC values in stroke participants will be greater than MC values in healthy controls during baseline blocks (t-test).

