10.4.2 Analysis of the Primary Efficacy Endpoint(s)

Primary study objective (change in RC, MC)

- Two-way ANOVAs on RC are conducted with within-subjects factor block (baseline, loading, retention) and between-subjects factor cohort (healthy, stroke). Three-way ANOVAs on MC are performed with within-subjects factors block and muscle (deltoid, biceps) and between-subjects factor cohort.

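### Sections 3.1 and 10.2 credit the baseline-to-loading change to gravity compensation or support, but the design estimates only assistance and resistance combined

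*Combined protocol and SAP*

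**What the plan says.** **What the trial claims to test.** The first primary objective in 3.1 is kinematic: "we will determine if gravity compensation can increase the reaching displacement of the impaired arm relative to the non-impaired arm". The second asks in the same way whether gravity compensation lowers the muscle activity that the task needs. Section 10.2 turns these into hypotheses about support, for example "Exoskeletal support will increase RC in stroke participants. Paired t-test comparing RC from baseline to loading blocks", with a parallel hypothesis that MC falls. Section 2.2 fixes the narrower term: "Gravity compensation is defined as the application of torque to the shoulder that counteracts the torque due to gravity".

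**What participants receive.** Section 4.1 says that in block 2 "bilateral exoskeletons apply gravity assistance to the impaired arm for stroke survivors and gravity resistance to the non-impaired arm". Controls get the same pairing, with assistance to the non-dominant arm and resistance to the dominant arm. Section 4.1 (Exoskeleton device) sets both loads at a 50% change in arm weight. Section 6.1 says that the two are applied at the same time and that resistance torque acts in the direction of gravity. Block 1 is unloaded, and "Block 3 is a retention block, where tested procedures are identical to block 1".

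**How it is analysed.** Section 10.2 uses paired t-tests of baseline against loading. Section 10.4.2 adds a block-by-cohort ANOVA for RC. For MC, "Three-way ANOVAs on MC are performed with within-subjects factors block and muscle (deltoid, biceps) and between-subjects factor cohort".

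**The concern.** By the definition in 2.2, resistance is not gravity compensation: it adds to gravity instead of opposing it. The objectives and hypotheses therefore credit one component of a two-component load, and the design never delivers that component alone.

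This bears directly on the kinematic endpoint. The target is hit with a shared cursor: "A cursor, located at the midpoint of the hands, will be used to" hit it. Section 3.1 describes the outcome as one arm's displacement relative to the other's. A load that holds back the non-impaired arm can therefore move the outcome in the hoped-for direction without any benefit from support.

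Section 4.2.1 sets the bar: "The primary endpoints will be a 2% increase in RC and a 5% decrease in MC". If RC rose by that amount and the t-test was significant, the 10.2 hypothesis as worded would be met, and the report would say that support raised RC. The data could not show that. A follow-on device giving assistance only could then rest on an effect never demonstrated for assistance. A null result would be no more specific: it would not show that gravity compensation alone has no effect.

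**Working it through.** **1. The plan's own load figures.** The inputs are the two linear torque formulas and the worked example in 6.1.5.

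- Assist: 5 × 1.089 + 2 × 0.16 − 0.13 = 5.635 Nm (printed 5.64 Nm, 50.7% of gravity torque).
- Resist: 6 × 0.722 + 3 × 0.17 + 0.70 = 5.542 Nm (printed 5.54 Nm, 49.8%).

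Both reproduce. The difference in load between the arms is 50.7 + 49.8 = 100.5% of one arm's gravity torque. Assistance supplies 50.7/100.5 = 50.4% of it and resistance 49.8/100.5 = 49.6%. So about half of the imposed asymmetry lies outside the 2.2 definition. This is a statement about load. It does not say that half of any change in RC or MC comes from resistance.

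**2. Can any planned comparison separate the two?**

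| Block | Impaired / non-dominant arm | Non-impaired / dominant arm |
|---|---|---|
| 1 Baseline | no load | no load |
| 2 Loading | about 50% assistance | about 50% resistance |
| 3 Retention | no load | no load |

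Write A for the effect of assistance, R for that of resistance and AR for any interaction.

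- Block 2 minus block 1 estimates A + R + AR, plus any order effect.
- Block 3 is unloaded, so it adds no information on A alone.
- Controls receive the same pairing, so a cohort-by-block interaction compares the combined effect between groups.
- The 10.4.2 block factor has only these three levels.

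A is not identified by any contrast in the plan.

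**3. Could R alone move RC?** Let h_i and h_n be the two hands' displacements along the target direction. The cursor moves (h_i + h_n)/2. To bring it to a given point, h_i + h_n must reach a given total. If resistance shortens h_n by some amount, h_i must lengthen by the same amount, and a measure of h_i relative to h_n rises. This gives a mechanism and a direction, not a size. It assumes that the cursor ends at a set point, whereas 4.1 has participants reach through the target.

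**4. Could R alone move MC?** Section 3.1 speaks of muscle activity on both sides, the documents give no MC formula, and the 10.4.2 model has muscle but not arm as a factor. If MC pools the arms, resistance could raise activity on the resisted side and hide a fall on the assisted side. If MC is defined otherwise, the direction may differ. It cannot be settled from the text.

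**5. Is the sample size affected?** No. The 10.5 range reproduces for a repeated-measures ANOVA with two groups and three blocks, with λ = f² × N × 3/(1 − ρ). Here ρ = 0.5 and sphericity are my assumptions. f = 0.25 gives N = 28 (λ = 10.5, power 0.812) and f = 0.30 gives N = 20 (λ = 10.8, power 0.812). That N applies to the combined effect, which is what the tests estimate.

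**The case against.** The best defence is that this is a matter of naming. Both modes are stated openly in 4.1, 6.1 and 6.1.5. The hypothesis in 2.3, the independent variable in 10.3 and the general approach in 10.4.1 already speak of loading. Section 2.4.2 presents the idea as rebalancing effort between the arms, which fits the combined load. The 10.2 hypotheses name the loading block in the same line, so support could be read as shorthand. The trial is a pilot, and 2.2.1 reports no significant group change in RC or MC in 14 stroke participants with these devices, so an over-read positive result may never arise.

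Much of this stands. Nothing is concealed, and no delivered load is in dispute. But describing the setup does not correct an objective that credits one component, and the shorthand reading is hard to hold when 2.2 gives the narrower term a definition and 3.1 uses it. Pilot status is a reason to reword instead of adding blocks.

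Three stronger readings are tempting and are not supported:

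- A reader might convert the 2% RC endpoint into a required shortening of the resisted arm's reach and take that as the size of the problem. With a fixed total displacement, that conversion only restates the endpoint and would be identical in an assistance-only design. It would also need an RC formula and a baseline share, and the documents give neither.
- A reader might infer that resistance also inflates the fall in MC. The documents do not fix even the sign.
- A reader might infer that the tests are invalid or the study too small. They are tests of combined loading, and the stated N is unaffected.

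**Conclusion.** The point holds as one of attribution. Under the plan, the baseline-to-loading change in RC and MC is the effect of assistance and resistance together, and no planned comparison isolates gravity compensation. As worded, 3.1 and 10.2 allow a causal conclusion that the design cannot give.

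For RC there is a plausible route by which resistance alone would raise the endpoint. It rests on the midpoint cursor and on the description of RC in 3.1 as one arm relative to the other. Its size cannot be computed from the documents. For MC the attribution problem is the same, but the direction of any resistance effect is unknown. What is affected is the conclusion that may be drawn, not the tests, the procedures or the sample size.

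**What to change.** In 3.1, in 10.2 and in the Protocol Summary objective, replace gravity compensation or exoskeletal support, as the named cause, with combined exoskeleton loading. Define it once as about 50% assistance to the impaired (or non-dominant) arm given together with about 50% resistance to the non-impaired (or dominant) arm.

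Add one sentence to 3.1 and 10.2, along these lines: *The design does not separate assistance from resistance, and no conclusion will be drawn about gravity compensation alone.*

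The cost is text only. There is no new block, no new data, and no change to the tests, session length or sample size. Separating the components would need assistance-only and resistance-only blocks in counterbalanced order. That is a question for a later study and is not proposed here.
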